X¹⁷ Test for FVIII trough and recovery. Trough is mandatory for all patients on the prophylaxis regimen, except at visit 1 and at the dispensing visit (except if the patient has a low titer inhibitor) it is also mandatory when determining half-life for inhibitor patients at an unscheduled visit. Recovery is optional, except if the patient has a positive inhibitor test (≥ 0.6 BU (Bethesda unit)) or there is suspicion of inhibitors. or the patient has performed PK at visit 2 then recovery must be performed at visit 8 . or before surgery, except if a PK has been performed previously in the trial or when determining half-life for inhibitor patients in the unscheduled visit, see section [8.5.2.3](#)

X¹⁸ Injection of trial product and recovery at the end of trial visit will be reported in the extension trial

X¹⁹ Trough and recovery if the patient has a low titer inhibitor (≥ 0.6 BU and ≤ 5 BU)

X²⁰ FVIII activity.

X²¹ If a second confirmatory inhibitor test must be taken

X²² If there is a follow-up visit after end of trial, the case book must be signed at the follow-up visit

X²³ Only to be performed if the patients withdraw from the trial during the main phase of the trial

Table 2–2 Pharmacokinetic flowchart

	Nominal time			Visit 2 0-11 years	Visit 2 ≥12 years
	hours	min	Sample window (min)		
Day1	-01	00	+55	X	X
	00 ²	00 ²		X ¹	X ¹
	00	15	±5		X
	00	30	±5	X	X
	01	00	±10		X
	04	00	±60	X	X
	08	00	±60		X
	12	00	±60		X
Day 2	24	00	±120	X	X
	30	00	±120		X
Day 3	48	00	±120		X

X¹ Patient must be dosed with 50 ±5 IU/kg body weight (BW) trial product

X² Time of dosing is equal to the stop time of injection

3 Background information and rationale for the trial

The trial will be conducted in compliance with this protocol, International Conference on Harmonisation (ICH) Good Clinical Practice (GCP)¹ and applicable regulatory requirements, and in accordance with the Declaration of Helsinki.²

In this document, the term investigator refers to the individual responsible for the overall conduct of the clinical trial at a trial site.

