5.2 Rationale for trial design

This is an uncontrolled, non-randomised trial and the design is common for trials with FVIII products in haemophilia A patients. In this trial, previously treated severe haemophilia A patients will receive routine prophylaxis treatment and treatment of bleeds, as well as prevention and treatment of bleeding episodes in surgery. This design is to a large extent similar to the pivotal NN7008-3543 (guardian™1) and NN7008-3568 (guardian™2) trial design. The patients will be treated for approximately 6 months in the main phase which will allow both patients on prophylaxis and on-demand treatment to accumulate sufficient exposures to turoctocog alfa in order to demonstrate efficacy and safety in treatment and prevention of bleeding episodes. If a patient has not finalised the main phase at the time of cut off for the main CTR they will be moved to the extension phase of the trial and thus will not have 6 months in the main phase of the trial. See [Figure 16–1](#)

This trial will also include a PK session at visit 2 to characterise the PK profile in Chinese population. This trial is conducted in a Chinese population and will be comparable to the pivotal trial in the guardian program.

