6.1 Number of patients – planned and required

- Number of patients planned to be screened: 70
- Number of patients planned to start on trial product: 65
- Number of patients planned to complete the main trial: 60
- Number of patients planned to complete the extension trial: 50

Completed patients in the main trial are defined as having completed visit 8. If a patient is withdrawn during the main part of the trial they are not counted as completers, except if they are withdrawn due to inhibitor development.

PK phase (Visit 2):

Assessment of a single dose PK profile at visit 2 is required in at least 12 patients and maximum 18 patients.

- At least 3 patients aged 0-5 years and maximum 6 patients
- At least 3 patients aged 6-11 years and maximum 6 patients
- At least 6 patients aged 12 and older and maximum 12 patients

Not all age groups can reach the maximum numbers of patients as the total number can only be 18 patients.

If a patient has started in the PK phase, but has not completed most of the blood samples he will not be counted as a PK patient, and a new PK patient must be enrolled into the PK part.

Main phase:

- At least 10 patients to complete the on-demand regimen
 - At least 12 patients planned to start on on-demand regimen
- At least 20 patients to complete the prophylaxis regimen
 - At least 22 patients planned to start on the prophylaxis regimen

Table 6–1 Patients planned to be dosed

	PK phase	Main phase	Extension phase
Age (years)	#patients		
0-5	3-6	on-demand 12-43 prophylaxis 22-53	No requirement
6-11	3-6		
≥12	6-12		
All	12-18	65	No requirement

See above [Table 6–1](#) for the minimum and maximum requirements of patients to start on trial product. The numbers in this table will be used to stop the screening of patients, see section [7](#). All patients already screened and who are eligible will be enrolled, which may cause the maximum numbers in [Table 6–1](#) to be exceeded.

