- Next visit should be scheduled

8.1.2.1 PK at visit 2

Blood sampling for PK will be performed during a period of 48 hours for patients who are 12 years and older and 24 hours for children below the age of 12 years, see [Table 2-2](#) for the specific sampling time points. It is not required that the patient stay overnight.

PK sampling must start after the assessments performed at visit 2. See section [8.3.4](#) for more information in regards to the PK sampling.

Patients must not be dosed with FVIII or other products containing FVIII before the PK session, see [Table 8-1](#) for the required washout periods as this is dependent of the age.

Key reminders:

- Check for adequate washout periods of FVIII products before the trial product injection, see [Table 8-1](#) and for other rescheduling criteria, see section [8.3.4](#)
- PK dose is 50 ±5 IU/kg BW

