Table 8-8 Definition of PK parameters

Parameter	Description	Calculation
$t_{1/2}$ (hours)	Terminal half-life	$t_{1/2} = \ln(2) / \lambda_z$, where λ_z is the terminal elimination rate. The terminal elimination rate will be estimated using linear regression on the terminal part of the time vs. log(concentration) curve
AUC_{last} ((IU*h)/mL)	Area under the plasma concentration vs. time curve from time zero to the last measurable concentration	AUC_{last} is calculated using the linear trapezoidal method from time 0 to the time for the last measurable concentration. The concentration at time 0 will be estimated by log-linear extrapolation of the two initial post-administration concentrations (see below) and used in the calculation of AUC_{last} .
Incremental Recovery ((IU/mL)/(IU/kg))	Peak level recorded 30 min. after end of infusion, adjusted for pre-administration concentration ([IU/mL]/[IU/kg])	The incremental recovery is calculated as (FVIII:C activity measured in plasma 30 min after dosing - FVIII:C activity measured in plasma immediately before dosing) / (dose injected at time 0 min), where the dose is expressed as IU FVIII product per kg BW.
AUC_{0-inf}	Area under the concentration vs. time from time curve zero to infinity	$AUC_{0-inf} = AUC_{last} + (C_{(t)} / \lambda_z)$, where $C_{(t)}$ is the last measurable concentration.
AUC%Extrap	The extrapolated part of AUC_{0-inf}	$100 \cdot (C_{(t)} / \lambda_z) / AUC_{0-inf}$. This is not a PK parameter. It is only a description of the extent of extrapolation in the AUC calculation.
C_{max} (IU/mL)	The maximal concentration	The maximal observed concentration. Note that this will likely be obtained at the first measurement and will be sensitive to deviations from the scheduled sampling time. This limits the value of this parameter, especially when comparing to other studies.
CL (mL/h/kg)	Total plasma clearance of drug after intravenous administration	$CL = \text{Dose} / AUC_{0-inf}$

Parameter	Description	Calculation
MRT (hours)	Mean Residence Time	$MRT = AUMC/AUC_{0-inf}$, where AUMC is the area under the first moment curve, i.e. the area under the curve $t \cdot C(t)$, calculated with the same method as AUC (linear trapezoidal method + extrapolated area).
V_{ss}	Apparent volume of distribution at equilibrium	$V_{ss} = CL \cdot MRT$
V_z	Apparent volume of distribution based on the terminal phase	$V_z = CL/\lambda_z$

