#### **Pharmacokinetic endpoints**

- PK endpoints after a single dose of turoctocog alfa:
  - Incremental recovery of FVIII
  - Area under the curve ( $AUC_{0-inf}$ )
  - Half-life ( $t_{1/2}$ )
  - Clearance (CL)
  - Highest measured FVIII activity in the profile ( $C_{max}$ )

The PK endpoints will be presented by the mean, standard deviation, minimum and maximum value, the geometric mean and 95% confidence interval for the geometric mean.

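### The linear trapezoidal rule, applied to three post-dose samples in children under 12, overstates AUC0-inf and understates clearance, more so than in older patients

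*Protocol*

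**What the plan says.** Protocol section 8.3.4, Table 8-8, defines the PK calculations. AUC_last "is calculated using the linear trapezoidal method from time 0 to the time for the last measurable concentration". AUMC, which feeds MRT and Vss, is "calculated with the same method as AUC (linear trapezoidal method + extrapolated area"). The starting value C(0) is extrapolated back log-linearly from the first two post-dose samples. For the terminal rate, "The terminal elimination rate will be estimated using linear regression on the terminal part of the time vs. log(concentration) curve". AUC0-inf is AUC_last plus C(t)/λz, and CL is dose divided by AUC0-inf.

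Table 2-2 sets the sampling times. The column "Visit 2 0-11 years" has post-dose samples at 0.5, 4 and 24 h only. The column for 12 years and over has nine, at 0.25, 0.5, 1, 4, 8, 12, 24, 30 and 48 h. Section 8.1.2.1 confirms the durations: "Blood sampling for PK will be performed during a period of 48 hours for patients who are 12 years and older and 24 hours" for younger children.

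AUC0-inf and CL are named PK endpoints in protocol sections 4.2.2.1 and 16.4.3 and in the SAP. The SAP gives summary statistics ("The PK endpoints will be presented by the mean, standard deviation, minimum and maximum value", plus the geometric mean with its 95% confidence interval) but no AUC rule, and its section 3 reports no departure from the protocol. Neither document says whether the PK summaries are pooled over age or split.

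**The concern.** The plan treats the decline as log-linear when it estimates C(0) and λz, then joins the same points with straight lines when it integrates. With closely spaced samples this does little harm. With one 20-hour gap it does: the chord from 4 to 24 h lies well above the curve, and the excess area goes straight into AUC0-inf and, inversely, into CL.

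The error differs by age group only because the schedules differ. With identical true clearance in both groups, the reported clearance would still be lower in children. If the groups are pooled, the summary depends on the age mix. Section 6.1 caps the PK session at 18 patients and allows 3 to 6 patients in each of the two younger groups, with "At least 6 patients aged 12 and older and maximum 12 patients". A full session can therefore run from 6 children and 12 older patients to 12 children and 6 older.

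AUC0-inf and CL are at stake, together with MRT, Vss and Vz, which are in Table 8-8 but are not named endpoints. Incremental recovery, Cmax and half-life do not use the trapezoidal rule and are unaffected.

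**Working it through.** The plan states no AUC, CL or half-life value, so there is no figure of its own to reproduce. The check applies Table 8-8 to known curves at the nominal Table 2-2 times and compares the result with the exact integral.

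**Assumptions.** Mono-exponential decline C(t) = exp(−kt), k = ln 2 / half-life, C(0) = 1. Half-life 7 to 12 h is an assumption. λz is fitted on the last three points.

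**Formulas.**
- Linear segment: (t2 − t1)(C1 + C2)/2
- Log segment: (C1 − C2)(t2 − t1)/ln(C1/C2)
- AUC0-inf = sum of segments + C(t)/λz; true value 1/k
- CL error = (true AUC / calculated AUC) − 1

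**Worked example, children, half-life 8 h.** k = 0.0866; true AUC = 11.54. Concentrations at 0, 0.5, 4 and 24 h are 1, 0.958, 0.707 and 0.125.

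| Piece | Linear rule |
|---|---|
| 0 to 0.5 h | 0.5 × (1 + 0.958)/2 = 0.49 |
| 0.5 to 4 h | 3.5 × (0.958 + 0.707)/2 = 2.91 |
| 4 to 24 h | 20 × (0.707 + 0.125)/2 = 8.32 |
| Tail | 0.125/0.0866 = 1.44 |
| Total | 13.17 |

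13.17/11.54 gives AUC +14.1%, and 11.54/13.17 gives CL −12.3%. The exact 4 to 24 h area is (0.707 − 0.125)/0.0866 = 6.72, so that one segment adds 1.60, which is 13.9% of the true total. The log rule on the same segment gives 6.72.

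**Age 12 and over, half-life 8 h.** The nine-sample schedule gives 11.97 against 11.54: AUC +3.8%, CL −3.6%.

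**Across the assumed range:**

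| Half-life | AUC0-inf, <12 y | AUC0-inf, ≥12 y | CL, <12 y | CL, ≥12 y | Reported CL ratio, child to older, if truly equal |
|---|---|---|---|---|---|
| 7 h | +18.1% | +4.3% | −15.3% | −4.1% | 0.88 |
| 8 h | +14.1% | +3.8% | −12.3% | −3.6% | 0.91 |
| 10 h | +8.9% | +2.9% | −8.2% | −2.8% | 0.94 |
| 12 h | +6.0% | +2.2% | −5.6% | −2.2% | 0.96 |

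At equal half-life the AUC error in children is 4.2, 3.8, 3.1 and 2.7 times that at 12 and over. Outside this range the direction is the same: +23.7% against +4.9% at 6 h, and +4.2% against +1.8% at 14 h.

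**Pooled mean CL, half-life 8 h in everyone.** With 6 children and 12 older: (6 × −12.3 + 12 × −3.6)/18 = −6.5%. With 12 children and 6 older: (12 × −12.3 + 6 × −3.6)/18 = −9.4%.

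**AUMC.** The curve t·C(t) peaks at 1/k (11.5 h at a half-life of 8 h), so in children the 4 to 24 h chord cuts below it. AUMC is too low while AUC is too high. Over half-lives of 7 to 12 h, MRT is understated by 28% to 13% and Vss by 39% to 18% in children; at 12 and over, MRT by 3% to 4% and Vss by 5% to 8%.

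**Robustness.**
- Sampling windows (±5 min, ±60 min, ±120 min), half-life 8 h: the children's AUC error runs from +9.1% to +20.8%. The log rule gives 0% at every corner.
- Bi-exponential shapes (assumed fast phase 20–40% with half-life 1–3 h, terminal 7–12 h). Children: linear +4.9% to +25.6%, log −1.9% to +3.3%. Age 12 and over: linear +2.5% to +5.5%, log +0.1% to +1.0%.
- Assumed 10% log-normal assay error, half-life 8 h, 20,000 runs. The median AUC error in children is +14.4% linear and +0.2% log; at 12 and over it is +4.2% and +0.3%. The SD of log AUC in children is 6.7% linear and 6.3% log, so the log rule costs no precision.

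**The case against.** The linear rule is clearly pre-specified and is a recognised method. PK is supportive and descriptive in 12 to 18 patients, and the plan contains no comparison of children with older patients and no PK hypothesis. The concentrations are kept, so either rule can be applied at reporting. All of this stands and limits the consequence. It does not remove the error: with no test planned, the point estimates are the result, and they are what is biased.

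The stronger objection is comparability. Section 5.2 says this trial "will be comparable to the pivotal trial in the guardian program", and section 16.1 says it is to supplement results from non-Chinese patients. If those trials used the linear rule, changing it here loses a like-for-like comparison. The documents do not say which rule they used. Keeping the linear result as a sensitivity analysis meets this point.

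The size is conditional, which also stands. At half-lives of 16 and 20 h the children's AUC error falls to +3.0% and +1.7%. At one extreme shape (50% fast phase with a 1 h half-life, terminal 16 h) the net linear error was −2.6% and the log error −6.6%. That case lies outside the 7 to 12 h range, and its negative sign comes from the three-point λz fit, not from the trapezoid.

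**Conclusion.** The concern holds. For AUC0-inf and CL, the direction and the larger error in children are well supported: they appear for mono-exponential decline at every half-life tested from 6 to 14 h, and across the bi-exponential shapes with a terminal half-life of 7 to 12 h. The size rests on the assumed half-life and shape. For mono-exponential decline at 7 to 12 h, AUC0-inf is overstated by 18% to 6% in children against 4% to 2% in older patients, and the schedule alone lowers the reported child-to-older CL ratio to between 0.88 and 0.96 if true clearance and half-life are equal. The trial's primary conclusion is not touched. This is a systematic and removable error in two named endpoints, and it should be corrected.

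**What to change.** In Table 8-8, replace the linear rule for AUC and AUMC with the linear-up/log-down trapezoidal rule: logarithmic on every declining concentration segment, including the one from C(0), and linear elsewhere. For AUMC the log segment is (t1C1 − t2C2)/k + (C1 − C2)/k², with k = ln(C1/C2)/(t2 − t1). State the rule under the SAP's pharmacokinetic endpoints and list it in SAP section 3 as a change. Report the linear-rule result as a sensitivity analysis for comparison with other trials. Summarising the PK endpoints separately for under 12 and for 12 and over would also help the reader, but the correction does not depend on it.

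The cost is a few lines of text and one extra run of the PK calculation, with no additional blood. The change does not cure the other limits of three samples: λz in children still rests on two or three points, and at a 12 h half-life about a quarter of AUC0-inf is extrapolated.

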8.3.5 Surgery

For patients who require surgery during the trial, relevant treatment and assessment will be performed and recorded. The treatment regimen will be given by the investigator or surgeon (guided by the investigator), see [Table 5-3](#).

The following data must be recorded for surgery, see [Table 8-9](#). Minor and emergency surgery requires less information to be recorded:

Table 8–9 Surgical intervention

Surgery information	Planned Major	Planned Minor	Emergency Minor/Major surgery
Surgery type , see Table 8–10	X	X	X
Surgical indication	X	X	X
Surgical procedure	X	X	X
Surgery location	X	X	X
Start date and time of surgery	X	X	X
Stop date and time of surgery	X	X	X ¹
Haemostatic response after surgery, see Table 8–12	X	X	X ¹
Haemostatic response during surgery, see Table 8–11	X	X	X ¹
Actual blood loss during surgery, see Table 8–13	X		X ¹
Estimated blood loss during surgery, see Table 8–13	X		X ¹
Blood and blood products transfusion quantity	X		X ¹
Blood and blood products transfusion type	X		X ¹

X¹ If possible

Emergency surgery is allowed in this trial if adequate supply of trial product is available. . The investigator can decide which trial assessments can be made in an emergency situation, except for the above information mentioned in the “Emergency minor/major surgery” column.

The patient must be withdrawn from the trial in case he is treated with another FVIII concentrates than turoctocog alfa during the surgery, please see the allowed products during surgery in section [8.2.1](#). Also patients with a low titer inhibitor (≥ 0.6 BU and ≤ 5 BU) must be withdrawn from the trial if they need surgery.

The patient may have a PK (see [8.3.4](#)) performed before the surgery at an unscheduled visit at the discretion of the investigator.

A negative inhibitor test result and a satisfactory recovery test from central laboratory must be performed prior to the surgery day. It is expected that 2 weeks is the approximate time for laboratory results to be analysed and reported from central laboratory. If this cannot be achieved with a scheduled visit, then the patient must be called in for an unscheduled visit. An exception from this is emergency surgery.

Only 10 planned major surgeries in total may be performed during the main phase of the trial, after this all planned surgeries must be performed in the extension phase of the trial.

Table 8–10 Definition of surgery type

Surgery type	Definition
Major surgery	
is any invasive operative procedure where any one or more of the following occur
 
• A body cavity is entered.• A mesenchymal barrier (e.g. pleura, peritoneum or dura) is crossed.• A fascial plane is opened.• An organ is removed.• Normal anatomy is operatively altered 
These procedures may be performed using general anaesthesia, spinal anaesthesia, epidural anaesthesia, conscious sedation or with a combination of these modalities

Minor surgery	
is any invasive operative procedure in which only skin, mucous membranes, or superficial connective tissue is manipulated. Examples of minor surgery include vascular cutdown for catheter/fistula placement, implanting pumps or CVAD in subcutaneous tissue, biopsies or placement of probes, leads, or catheters requiring the entry into a body cavity only through a needle/guidewire.

Dental surgery will be classified as minor or major based on above definitions

Table 8–11 Haemostatic response during surgery

Category	Definition
Excellent	blood loss less than expected
Good	blood loss as expected
Moderate	blood loss more than expected
None	uncontrolled bleeding

This evaluation must be performed by the surgeon

Table 8–12 Haemostatic response after surgery

Category	Definition
Excellent	Better than expected in this type of patient and procedure
Good	As expected in this type of patient and procedure
Moderate	Less than optimal for the type of procedure, maintained without change of treatment regimen
None	Bleeding due to inadequate therapeutic response with adequate dosing, change of regimen required

This evaluation will most likely be assessed by the investigator, but could also be the surgeon.

The haemostatic response after surgery is only measured once at the last day of the post-operative period the patient is at the trial/surgery site.

Table 8–13 Definition of blood loss

Blood loss	Definition
Actual blood loss (mL)	during the procedure as recorded in surgical procedure report (or chart) by the surgery team (surgeon and anaesthesiologist)
Estimated blood loss (mL)	blood loss for similar procedures in non-haemophilia and haemophilia (if available for this type of procedure) patients undergoing the same type and extent of surgical procedure stated before the procedure by the surgery team (surgeon and anaesthesiologist)

8.3.6 Patient reported outcomes

Disease and age specific health related quality of life (HRQOL) will be collected through use of the patient reported outcome (PRO) instruments HAEM-A-QOL (for adults) and HAEMO-QOL (for children/adolescents and their parents) at visit 2 and 8 in the main phase of the trial and in the assessment visit, though only annually and at the end of trial visit in the extension phase of the trial.

Table 8–14 Patient reported outcome questionnaires by age group

Name	Age group (years) (patient age in years at baseline)	Comment
HAEM-A-QOL	17 and older	To adults
HAEMO-QOL	13-16	To adolescents and parents
HAEMO-QOL	8-12	To children and parents
HAEMO-QOL	4-7	To parents
	0-3	No PRO questionnaire

The patient’s age at the time when he or his parent/LAR signs the informed consent, determines which age group he belongs to and consequently which PRO questionnaire that should be used throughout the trial. The same PRO questionnaire should be used during the whole trial including in the extension phase and even if the patient grows into another age group during the conduct of the trial. If parents/caregiver stop accompanying a patient to visits they do not have to fill in the HAEMO-QOL parent version.

The questionnaires were originally developed in UK in English and have been translated and linguistically validated into simplified Chinese. The questionnaire must be filled in at visits 2 and end of trial in the main phase. In the extension phase it must be filled in annually and at the end of trial visit, preferably before any other trial-related procedures.

When PROs are filled in by the patient, these must be reviewed by the investigator to ensure that AEs, including any overall change in health and concomitant medication, are reported, see section [11](#). This review must be documented in the patient's medical record.

If clarification of entries or discrepancies in the PROs is needed, the patient must be questioned and a conclusion made in the patient's medical record. Care must be taken not to bias the patient.

The completed PRO questionnaires (top page) must be sent to data management in India by the monitor for data entry into the clinical database. The copy (bottom page) must be retained by the site.

